2. INTERIM AND FINAL ANALYSES

In this study, interim analyses for periodic safety update report will be performed periodically. At the time of interim analyses, only the analyses of items necessary for periodic safety update report among the statistical analyses specified in this plan will be performed. In addition, the final analysis for the application for reexamination will be performed. At the time of the final analysis, all analyses specified in this plan will be performed.

3. HYPOTHESIS AND DECISION RULES

3.1. Statistical Hypothesis

Because this study is not a confirmatory investigation, the tests are considered exploratory and a p-value resulting from a test will be considered as a descriptive statistic with no significance level specified, although a post-hoc threshold value may be introduced for a screening purpose.

3.2. Statistical Decision Rules

Not applicable.

4. ANALYSIS SETS

4.1. Safety Analysis Set

The safety analysis set consists of the patients who meet the inclusion criteria for this study and are confirmed to have received at least one dose of Mycobutin. However patients who have received treatment with Mycobutin before marketing (those who discontinued or completed their treatment with Mycobutin before the marketing of Mycobutin[®] 150mg Capsules) will be excluded from the safety analysis set.

4.2. (Preventive) Effectiveness Analysis Set

Among the patients in the safety analysis set, those who received Mycobutin for the prevention of MAC infection and underwent an effectiveness evaluation (determination of whether an onset of MAC infection is observed or not) comprise the (preventive) effectiveness analysis set.

4.3. (Therapeutic) Effectiveness Analysis Set

Among the patients in the safety analysis set, those who underwent at least one post-treatment effectiveness evaluation (determination of bacteriological response or clinical efficacy at the end of the observation period) comprise the (therapeutic) effectiveness analysis set.

4.4. Bacteriological Response Analysis Set

Among the patients in the (therapeutic) effectiveness analysis set, those who underwent at least one bacteriological response determination comprise the bacteriological response analysis set. However, the patients with a bacteriological response determination for whom the result is considered inappropriate based on the results of the bacteriological tests will be excluded from the bacteriological response analysis set.

4.5. Subgroups

Subgroup analyses of safety will be performed for the following patient background factors:

- Sex [male, female]
- Pregnancy (in females) [absent, present]
- Age group 1 [<15 years, ≥15 years to <65 years, ≥65 years]
- Age group 2 [<20 years, ≥20 years to <30 years, ≥30 years to <40 years, ≥40 years to <50 years, ≥50 years to <60 years, ≥60 years to <70 years, ≥70 years to <80 years, ≥80 years]
- Primary disease [HIV infection, others]
- Race [Japanese, others]
- Hepatic dysfunction [absent, present]
- Hepatitis [absent, present]
- Renal dysfunction [absent, present]
- Past history [absent, present]
- Complications [absent, present]
- Ophthalmologic complications [absent, present]
- Baseline HIV-RNA copy number (copies/mL) [<200, ≥200 to <400, ≥400 to <10,000, ≥10,000 to <100,000, ≥100,000]
- Baseline CD4 count (cells/mm³) [≥0 to <100, ≥100 to <200, ≥200 to <350, ≥350 to <500, ≥500]
- Centers for Disease Control and Prevention (CDC) classification [A, B, C, P-0, P-1, P-2]

Subgroup analyses of safety will also be performed for the following other factors:

- Maximum daily dose [<150 mg, 150 mg, 300 mg, 450 mg, >450 mg]
- Mean daily dose [<150 mg, 150 mg, >150 mg to <300 mg, 300 mg, >300 mg to <450 mg, 450 mg, >450 mg]
- Duration of treatment [≤1 week, >1 week to ≤2 weeks, >2 weeks to ≤4 weeks, >4 weeks to ≤8 weeks, >8 weeks to ≤12 weeks, >12 weeks to ≤24 weeks, >24 weeks to ≤36 weeks, >36 weeks to ≤1 year, >1 year to ≤3 years, >3 years to ≤6 years, >6 years to ≤8 years, >8 years]
- Concomitant medications (anti-HIV drugs) [absent, present]
- Concomitant medications (anti-MAC drugs) [absent, present]

- Concomitant use of the combination of sulfamethoxazole and trimethoprim (SMX/TMP) [absent, present]

Subgroup analyses of effectiveness will be performed for the following patient background factors:

- Sex [male, female]
- Pregnancy (in females) [absent, present]
- Age group 1 [<15 years, ≥15 years to <65 years, ≥65 years]
- Age group 2 [<20 years, ≥20 years to <30 years, ≥30 years to <40 years, ≥40 years to <50 years, ≥50 years to <60 years, ≥60 years to <70 years, ≥70 years to <80 years, ≥80 years]
- Primary disease [HIV infection, others]
- Race [Japanese, others]
- Hepatic dysfunction [absent, present]
- Renal dysfunction [absent, present]
- Past history [absent, present]
- Complications [absent, present]
- Baseline HIV-RNA copy number (copies/mL) [<200, ≥200 to <400, ≥400 to <10,000, ≥10,000 to <100,000, ≥100,000]
- Baseline CD4 count (cells/mm³) [≥0 to <100, ≥100 to <200, ≥200 to <350, ≥350 to <500, ≥500]
- Centers for Disease Control and Prevention (CDC) classification [A, B, C, P-0, P-1, P-2]

Subgroup analyses of effectiveness will also be performed for the following other factors:

- Maximum daily dose [<150 mg, 150 mg, 300 mg, 450 mg, >450 mg]
- Mean daily dose [<150 mg, 150 mg, >150 mg to <300 mg, 300 mg, >300 mg to <450 mg, 450 mg, >450 mg]
- Duration of one prophylactic or therapeutic treatment [≤1 week, >1 week to ≤2 weeks, >2 weeks to ≤4 weeks, >4 weeks to ≤8 weeks, >8 weeks to ≤12 weeks, >12 weeks to ≤24 weeks, >24 weeks to ≤36 weeks, >36 weeks to ≤1 year, >1 year]
- Concomitant medications (anti-MAC drugs) [absent, present]
- Concomitant use of SMX/TMP [absent, present]

5. ENDPOINTS AND COVARIATES

5.1. Safety Endpoints

- Adverse drug reactions: adverse events (AEs) determined to be related to Mycobutin by the physician or Sponsor
- Adverse events: All-causality adverse events

- Major investigation items: The events of major investigation items will be identified according to a separate list that provides the event names corresponding to each specified AE.

5.2. Effectiveness Endpoints

5.2.1. Prophylactic Treatment

- Occurrence of MAC symptoms in patients treated with Mycobutin for the prophylaxis of MAC infection will be determined as

Absent, or
Present.

5.2.2. Therapeutic Treatment

- Clinical efficacy (overall improvement): After each continuous treatment or at the final fiscal year of registration (the end of observation), clinical efficacy (overall improvement) will be determined using the following categories:

1. Markedly improved
2. Improved
3. Slightly improved
4. Unchanged
5. Aggravated
9. Indeterminable

- Bacteriological response: After each continuous treatment or at the final fiscal year of registration (the end of observation), bacteriological response will be determined according to the following categories:

1. Eradicated
2. Decreased
3. Unchanged
4. Increased
9. Unknown

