- (1) For registered patients, the administration status of each drug by the end of March of each year based on medical records and medical charts such as test results and survey results on the clinical course such as abnormal changes in laboratory test values and adverse events noted during the survey period should be entered and send using the System during period between April and July by the investigator.
- (2) When inquiries on data entered were made by the CRO (data clarification request through the System or e-mail), the investigator should, as necessary, revise and send the entered data.
- (3) When drug treatment is discontinued due to reasons such as a patient’s death or transfer to another hospital, the investigator should enter and send the administration status of each drug until discontinuation, the clinical course such as abnormal changes in laboratory test values and adverse events, and autopsy status (if the outcome is death) using the System.
- (4) After completing entry and revision of all investigation items, the investigator should verify the contents of a CRF (original) printed out (provided) in (by) the CRO and then sign or affix a seal to the CRF.

5) Retention of the original CRF

The CRO will collectively retain all CRFs and registration forms.

- 6) Affixing a signature or seal to the Statement of Confirmation
  - (1) At the time of signing or affixing a seal to the CRFs, the CRO will prepare and bring the “Statement of Confirmation” to the investigator for confirming the survey patients. The Statement of Confirmation is intended “to ensure that survey patients are all patients at the site during the survey period”. The investigator should verify the Statement of Confirmation and then sign or affix his/her seal to it.
  - (2) The CRO will retain the original of the signed or sealed “Statement of Confirmation”, prepare the “Statement of Confirmation” for each drug based on those from all investigators, and send it to the applicable company.
  
- 7) Notifying adverse drug reactions (ADRs), etc.
  - (1) When ADRs, etc. (including those for which the causal relationship is unknown) suspected to be associated with drugs occurred, the investigator should immediately notify them to the CRO or enter required items in the “HRD Joint Survey - Spontaneous Report of ADRs, etc.” form, which is provided beforehand, and fax it to the CRO.  

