## 5. Survey Items

- 1) Common items (CRF for the drug use investigation)
  - (1) Background
  - (2) Prescribed anti-HIV drug
  - (3) Prescribed concomitant medications (including drugs for the treatment of HIV-related diseases)
  - (4) Concomitant therapies
  - (5) Patient’s outcome (at the discontinuation of the survey)
  - (6) HIV-RNA, CD4, Centers for Disease Control and Prevention (CDC) classification, changes over time in body weight, and HIV tropism
  - (7) Abnormal changes in laboratory test values
  - (8) Adverse events (including ADRs, abnormal changes in laboratory test values, and newly developed opportunistic infection)
  - (9) Relationship with the disease or drug (mandatory for the target drugs administered at the time of onset of the adverse event)
  - (10) Autopsy status (if the outcome is death)
  
- 2) Survey items by product (Separated CRF for Mycobutin Capsules)
  - (1) MAC infection, etc. (when Mycobutin Capsules is used for tuberculosis, non-tuberculous Mycobacterium infection including Mycobacterium avium complex (MAC) infection, and prevention of the development of disseminated MAC infection in patients with HIV infection)

- (2) Samtarel (atovaquone) (when Samtarel Oral Suspension 15% is utilized for treatment or prevention of development of *Pneumocystis pneumonia*)
- (3) Edurant Tablets (rilpivirine hydrochloride) (when Edurant Tablets are used)  
 Complera Combination Tablets (rilpivirine hydrochloride/tenofovir disoproxil fumarate/emtricitabine) (when Complera Combination Tablets are utilized)  
 Record measurement results and other relevant data if blood drug concentrations are measured.
- (4) Tivicay Tablets (dolutegravir sodium) and Triumeq Combination Tablets (dolutegravir sodium/abacavir sulfate/lamivudine) (when Tivicay Tablets or Triumeq Combination Tablets are used)
  - (i) Record measurement results and other relevant data if blood drug concentrations are measured.
  - (ii) When pilsicainide is concomitantly used, separately provide electrocardiographic data.
  - (iii) Record measurement results if a liver function test (e.g., alanine aminotransferase [ALT], aspartate aminotransferase [AST], alkaline phosphatase [AL-P], and total bilirubin [T-Bil]) is performed.
  - (iv) Record measurement results if a renal function test (e.g., serum creatinine, urine protein, urinary albumin, and tubular damage markers) is carried out.

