6. HANDLING OF MISSING DATA

Any missing value for a laboratory parameter or effectiveness endpoint will be handled as a missing value and no imputation will be carried out.

If the seriousness, measures taken, or outcome for an AE is missing, they are counted as “unknown”.

If a date such as the onset date of an AE is missing, handling of those data will be defined in separate statistical analysis specifications prepared for the drug use investigation of Mycobutin[®] 150mg capsules.

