10. APPENDIX

10.1. Appendix 1: Details of Data Collection

A1.1 Definition of visits

Visit	Endpoints	Definition [Allowance]
At start of treatment	HIV-RNA, CD4, CDC category, body weight, bacteriological tests	Data obtained before and on the day of the first dose (treatment start) of this survey. If there are multiple data, select data on the day closest to the first dose day of this survey.
At end of observation	Effectiveness endpoints	Data obtained on the day of the last dose of this survey or before and after the day. If there are multiple data, select data on the day closest to the last dose day of this survey.

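### The SAP does not say how a therapeutic course that ends in death is categorised, so deaths can drop out of the clinical response and eradication rates

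*SAP*

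**What the plan says.** **Timing and scales.** SAP 5.2.2 uses the same timing for both therapeutic endpoints: "After each continuous treatment or at the final fiscal year of registration (the end of observation), clinical efficacy (overall improvement) will be determined", and for bacteriology "After each continuous treatment or at the final fiscal year of registration (the end of observation), bacteriological response will be determined". The clinical scale runs from Markedly improved to Aggravated, plus Indeterminable. The bacteriological scale runs from Eradicated to Increased, plus Unknown. Neither has a category for death, and no text assigns death to an existing one. Appendix A1.1 anchors effectiveness data on the last dose: "Data obtained on the day of the last dose of this survey or before and after the day", taking the closest when there are several.

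**Who is analysed.** SAP 4.3 admits "those who underwent at least one post-treatment effectiveness evaluation (determination of bacteriological response or clinical efficacy at the end of the observation period"). SAP 4.4 further requires a bacteriological determination. SAP 6 says that a missing "effectiveness endpoint will be handled as a missing value and no imputation will be carried out".

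**Rates.** The clinical response rate (SAP 7.2.4.2) removes Indeterminable cases from its denominator. The eradication rate (SAP 7.2.4.3) removes Unknown. Both carry a 95% CI, exact under SAP 7.1.3.

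**Death in the data.** Protocol section 4, item 4)(3), treats death and transfer as reasons for stopping drug treatment and asks for drug administration status, clinical course and, for a death, autopsy status. Protocol section 5 lists the patient's outcome at the end of participation among the common CRF items. Nothing in SAP 7.2.4 uses that outcome.

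**The concern.** Evaluating therapeutic effectiveness is a stated objective in Protocol section 1, and the results go to reexamination and back to healthcare professionals. A reader of a response rate will assume that a patient who died during treatment without having responded counts against it. Here that depends on how the individual investigator filled in the form. One may enter Aggravated, which keeps the course as a non-response. Another may enter Indeterminable, or nothing, and the course disappears.

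Relative to counting these deaths as non-response, the effect goes in one direction: the numerator stays the same and the denominator shrinks. The confidence interval does not reflect this, because it is computed on the courses that remain.

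**Working it through.** **Step 1: follow a course that ends in death through the rules.**

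| How the death is recorded | Clinical response rate | Eradication rate |
|---|---|---|
| No rating of either kind | Out (SAP 4.3, 6) | Out (SAP 4.3, 4.4, 6) |
| Indeterminable (clinical) | Out (SAP 7.2.4.2) | Depends on the bacteriological rating |
| Unknown (bacteriological) | Depends on the clinical rating | Out (SAP 7.2.4.3) |
| Aggravated, Unchanged or Slightly improved | In, non-response | Depends on the bacteriological rating |
| Decreased, Unchanged or Increased | Depends on the clinical rating | In, not eradicated |

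The documents do not say which row applies. Two combinations are also unclear. If only the clinical rating is blank, the patient can enter the SAP 4.3 set through bacteriology, and the SAP 7.2.4.2 denominator removes only Indeterminable; whether SAP 6 then removes the blank is not stated. A patient with one rated course and a later unrated fatal course is in the set, because one evaluation is enough, but the handling of the second course is not stated.

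**Step 2: size.** The documents state no expected rate, number of courses or death rate, so there is no figure to reproduce. Let N be all therapeutic courses, D those dropped because of death (none with a documented response), R the responses, and d = D/N.

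- Reported rate = R/(N − D)
- All-course rate, with deaths as non-response = R/N
- Ratio = N/(N − D) = 1/(1 − d)

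This gives 1/0.95 = 1.05, 1/0.90 = 1.11, 1/0.80 = 1.25 and 1/0.70 = 1.43 for d of 5%, 10%, 20% and 30%.

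**Step 3: illustration.** Assumed: N = 100 and about 70% response among rated courses. Intervals are exact (Clopper-Pearson) 95%.

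| Dropped deaths | Reported rate (95% CI) | All-course rate (95% CI) | Gap, points |
|---|---|---|---|
| 5 | 66/95 = 69.5% (59.2 to 78.5) | 66/100 = 66.0% (55.8 to 75.2) | 3.5 |
| 10 | 63/90 = 70.0% (59.4 to 79.2) | 63/100 = 63.0% (52.8 to 72.4) | 7.0 |
| 20 | 56/80 = 70.0% (58.7 to 79.7) | 56/100 = 56.0% (45.7 to 65.9) | 14.0 |
| 30 | 49/70 = 70.0% (57.9 to 80.4) | 49/100 = 49.0% (38.9 to 59.2) | 21.0 |

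At about 50% response among rated courses, the gaps are 2.5, 5.0, 10.0 and 15.0 points. All these inputs are assumptions.

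**The case against.** **Timing.** A reader might infer that patients who die or transfer never reach a rating point, since SAP 5.2.2 names only the end of a continuous treatment or the final fiscal year. The documents do not support that. The protocol itself treats death and transfer as discontinuation, so the continuous treatment has ended. Appendix A1.1 works from the last dose and accepts data from before it. This objection stands in full. But A1.1 selects a date, not a category, so it does not settle how a death is scored.

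**Collection.** A reader might also infer that no rating is collected at discontinuation, because "the investigator should enter and send the administration status of each drug until discontinuation" and the items after it name none. That does not follow either. The routine annual list in the same section names none, yet ratings are plainly collected. The separate Mycobutin CRF and the HRD Standard Specifications cited in SAP 9 are not among the documents and may cover this.

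**Transparency.** SAP 7.2.1 counts exclusions from the effectiveness sets by reason, and the category counts in SAP 7.2.4 would show Indeterminable and Unknown. Some losses are therefore visible. They are not restored to the rates, and a death rated Indeterminable is not an exclusion and is not identified as a death.

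**Choice of scoring.** Counting every death as failure ignores cause of death and any response already documented. That is a fair reason not to put it in the main formula, and the fix below does not. SAP 3.1 calls the tests exploratory, but that does not define what an estimated rate includes.

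**Conclusion.** The point holds as a gap in scoring. No text says how a therapeutic course ending in death is categorised, and under SAP 4.3, 4.4, 6, 7.2.4.2 and 7.2.4.3 such courses can leave both rates. Where they do, the reported rate equals the all-course rate divided by (1 − d), and so is never lower than it.

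The size is unknown. The factors of 1.11 and 1.25 rest on assumed shares of 10% and 20% of courses dropped because of death, with none of those courses having a documented response. If investigators rate most deaths Aggravated, the effect on the clinical response rate is small. It would be wrong to conclude that the rates are known to describe survivors only, or that transferred patients are necessarily lost. The documents show that deaths can be omitted, not how often they are.

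**What to change.** Amend SAP 7.2.4.2 and 7.2.4.3 and leave the main formulas as they are.

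1. Using the patient-outcome item already collected, show therapeutic courses that ended in death as a separate row beside the rating categories.
2. Add a companion clinical response rate and a companion eradication rate, each with an exact 95% CI. These keep in the denominator, as non-response, courses ending in death without a documented response (for eradication, without documented eradication). State that these courses are included even where SAP 4.3 or 4.4 would leave them out.
3. For transfers, use any available rating closest to the last dose under Appendix A1.1, and report the number of unrated courses. No new CRF prompt is proposed. Registration for the therapeutic indications closed on March 31, 2015, before SAP version 4.0 of 24 June 2016, so a prompt could reach courses already ended only through retrospective queries.

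This assumes that the outcome item and the administration record together allow a death to be tied to a course; check that against the CRF. The cost is SAP wording and two extra rates, which will be somewhat lower than the main ones if any deaths are added back. Because the companion rates ignore cause of death, they should be read beside the main rates and not in place of them.

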5.3. Other Endpoints

Not applicable.

5.4. Covariates

In the analysis of safety, the presence or absence of contraindicated for coadministration (e.g., some azoles and macrolides) noted in PRECAUTIONS of the package insert as the drugs that require precautions for coadministration will be used as a covariate.

6. HANDLING OF MISSING DATA

Any missing value for a laboratory parameter or effectiveness endpoint will be handled as a missing value and no imputation will be carried out.

If the seriousness, measures taken, or outcome for an AE is missing, they are counted as “unknown”.

If a date such as the onset date of an AE is missing, handling of those data will be defined in separate statistical analysis specifications prepared for the drug use investigation of Mycobutin[®] 150mg capsules.

7. STATISTICAL METHODS AND STATISTICAL ANALYSIS

7.1. Statistical Methods

7.1.1. Analysis of Continuous Data

Summary statistics (number of patients, mean, standard deviation, median, minimum and maximum) will be calculated.

7.1.2. Analysis of Categorical Data

Categorical variables will be calculated by frequency and percentage.

7.1.3. Analysis of Binary Data

Binary variables will be calculated by frequency and percentage. Confidence intervals (CIs) for the percentages may also be calculated; in this case, the 95% CIs (two-sided) will be calculated using an exact method. Statistical tests may also be performed when appropriate; an association with a nominal variable will be tested by Fisher's exact test, and an association with an ordinal variable by the exact Cochran-Armitage test.

7.2. Statistical Analysis

7.2.1. Overview of Patients

- **Number of sites by establisher and number of patients**

In patients for whom the case report form was collected, the number and percentage of sites by establisher shown below and the number and percentage of patients will be calculated:

- University hospitals
- National hospitals established by the Ministry of Health, Labour and Welfare
- Prefectural and municipal hospitals
- Public organizations
- Hospitals established by corporations and individuals other than the above four
- General practitioners/clinics

In addition, the mean, minimum, and maximum of the number of patients per site will be calculated.

- **Disposition of patients**

In the patients for whom the case report form was collected, the number of those for whom the case report form was collected and those included in the safety analysis set will be tabulated. The patients excluded from the safety analysis set will also be counted in total and by reason for exclusion. In addition, Among the safety analysis set, the patients who are eligible for the effectiveness analysis will be counted for each of preventive and therapeutic treatments. The patients excluded from the effectiveness analysis set will also be counted in total and by reason for exclusion for each of preventive and therapeutic treatments. Total number of treated patients will be counted in a treatment-based manner for each of preventive and therapeutic treatments, because in this investigation, cases of multiple treatments in a single patient are expected to occur.

- **Listing of excluded patients**

Patients excluded from the safety analysis set and those excluded from the effectiveness analysis set will be tabulated with their reason for exclusion.

